Post-Emolic Rhythm Detection with Implantable versus External Monitoring (PER DIEM) Pilot Feasibility Study

Protocol/version #: 4.0
Current Version Date: February 22, 2016
Previous IRB Approved Version 3.1
Dates: Aug 13, 2015

CONFIDENTIAL

This document is confidential and the property of individual. No part of it may be transmitted, reproduced, published, or used by other persons without prior written authorization from the author.

Trial Registration ClinicalTrials.gov Identifier: NCT02428140

Per Diem Version 4.0

1

Summary of PERDIEM study protocol changes

Version	Date Approved	Changes from the previous version
1.0	Jan 29, 2015	Original protocol
2.0	March 18, 2015	
Changes from v1.0
 
 -inclusion minimum age changed from 50 to 18 years old -added requirement for at least 1 ECG as part of the etiologic workup -excluded patients with workup that included >48 hours of external ECG monitoring -allowed the inclusion of patients with transient deficits if CT/MRI showed evidence of infarction -removed plan for MRI scan at baseline and 12 months -removed cognitive testing from study visits -changed study visit schedule from 90 days and 1 year to 30 days, 6 months, 12 months
3.0	August 4, 2015	
Changes from v2.0
 
 -changed inclusion to specify that patients must be enrolled within 6 months of the index event
4.0	Feb 22, 2016	
Changes from v3.0
 
 -changed study visits from exclusively clinic-based to allow either clinic or telephone study visits -changed exclusion from “any condition with an indication for anticoagulation” to “any condition with an evidence-based indication for long term OAC”
4.0r	April 26, 2016	
Changes from v4.0
 
 -the device adjudication process and the study AF reporting document were amended to the protocol -the primary outcome was defined as definite atrial fibrillation lasting 2 minutes or more, including atrial flutter^a - removed the statement that the primary outcome requires a change in antithrombotic medication^b

^a The decision to change the study endpoint to **definite AF lasting 2 minutes or more, including atrial flutter** was finalized by the steering committee on April 26, 2016, before the adjudication of any device data. The change was made due to technical limitations of the AF detection algorithm for the Medtronic LINQ implantable loop recorder studied. The shortest time over which the LINQ device can make a reliable assessment for AF is 2 minutes. The new endpoint was indicated in an adjudication document that was attached to the protocol

^b There was consensus from study investigators that 2 minutes or longer of **definite AF** in the setting of a recent stroke was likely to always be clinically actionable. The requirement for a change in antithrombotic medication was felt redundant and removed from the endpoint description.

List of Abbreviations

ADC	apparent diffusion coefficient
AF	atrial fibrillation
CRF	case report form
CT	computerized tomography
CTA	computerized tomography angiogram
DWI	diffusion-weighted imaging
ECG	electrocardiogram
ELR	external loop recorder
FLAIR	fluid-attenuated inversion recovery
GRE	gradient recalled echo
ICD	implantable cardiac defibrillator
ILR	implantable loop recorder
MRA	magnetic resonance angiogram
MRI	magnetic resonance imaging
OAC	oral anticoagulant
OCSP	Oxfordshire Classification of Stroke Program
REB	research ethics board
TIA	transient ischemic attack
TOAST	Test of Orgaran in Stroke Trial

1.0 BACKGROUND AND RATIONALE

Stroke is a leading cause of death and disability worldwide. In Canada, there are approximately 38,000 ischemic stroke admissions to hospital per year with an average annual cost estimated at 2.8 billion dollars.(1) Cardiac embolism is the cause of approximately 25% of ischemic strokes(2) with majority of these due to atrial fibrillation (AF).(3) Cardio-embolic stroke event rates are projected to rise in the next three decades, as the prevalence of AF increases with an aging population. The diagnosis of AF in stroke patients is particularly important since it typically results in prescription of antiplatelet to oral anticoagulant (OAC) therapies(4) that have been shown to reduce the risk of recurrent stroke by up to 63%.(5)

AF can be difficult to detect as it is often intermittent (paroxysmal) and most patients are asymptomatic.(6) In 25-30% of ischemic strokes no cause is established despite thorough diagnostic workup (cryptogenic stroke). Undiagnosed paroxysmal AF has been hypothesized to be the cause of a substantial proportion of cryptogenic strokes. Furthermore, determining TIA/stroke etiology is imperfect and often is complicated by the presence of coexisting causes.(7) It is likely that a sizable number of patients in whom a TIA/stroke has been attributed to an abnormality other than AF (non-cryptogenic stroke) will have AF detected if adequately investigated with prolonged ECG monitoring.(8)

Given superiority of OAC therapy in secondary stroke prevention in AF, detection of paroxysmal AF in all regardless of putative mechanism is of particular clinical relevance. Intermittent ambulatory electrocardiographic (ECG) assessment (Holter) is typically used for detection of paroxysmal AF after a stroke. However, this approach has a very low diagnostic yield in detecting a clinically actionable ECG diagnosis (4%-6%).(9) Cardiac ultrasound (echocardiography) is also routinely ordered after a stroke, but has a diagnostic yield of only 1% and rarely alters clinical management.

It is typical for a patient to undergo multiple ECGs, Holters and an echocardiogram after a stroke at significant cost (> \$1,000), but low diagnostic yield (< 5%).

The question of whether prolonged ECG monitoring with an external event triggered external loop recorder (ELR) can improve the detection of paroxysmal AF after cryptogenic stroke was addressed in the recently completed EMBRACE trial.(10) In EMBRACE, paroxysmal AF (> 30 seconds) was detected in 16% of stroke patients compared to only 3% with a repeat 24 hour Holter. It is not known whether even more prolonged ECG recording will increase the diagnostic yield further. However, it is likely that extended monitoring will identify a greater number of patients with paroxysmal AF given the infrequent nature of AF. Nonetheless, this is being addressed in the CRYSTAL-AF trial in which stroke patients undergo 12 months of continuous rhythm monitoring using a surgically implanted subcutaneous implantable ECG monitor termed implantable loop recorder (ILR).(11)

ECG monitoring has evolved greatly. While 24 to 48-hour recordings were once the only option, with the EMBRACE and CRYSTAL-AF trials we expect extended ECG monitoring will become the standard of care in the work-up of patients with embolic stroke. Yet the ideal target stroke patient population and the most cost-effective strategy to translate these clinical trials into practice remains unclear.

Long-term external recorders offer the potential to detect AF at a modest increase in cost but they suffer from three limitations; namely signal quality, compliance, and time delays in getting the diagnostic information to clinicians. The other option for long-term ECG monitoring is an ILR device. For example, the Medtronic LINQ REVEAL is a new miniaturized recorder that can be implanted in the outpatient clinic setting and is associated with minimal risks. It is linked to a wireless remote monitoring system, allowing long-term high quality ECG recordings and the capacity for early detection of AF and implementation of augmented antiplatelet or OAC where appropriate. This system is equipped with remote cardiac rhythm monitoring, where the collection of device data occurs in the patient's home with minimal patient interaction (i.e., wireless transmission). Cardiac rhythm data are then uploaded to a secure site for review, and appropriate intervention. ILR has disadvantages; specifically they are invasive, non-reusable and carry a significant upfront cost. While ILR may provide a more comprehensive estimate of the total burden of AF the clinical relevance is unclear. Furthermore, there are no data on the relative cost-effectiveness of ILR versus an ELR for the diagnostic work-up after a stroke.

Whether the additional cost of an ILR is warranted, the relative diagnostic accuracy of external versus internal ECG assessment, compliance with external ECG monitoring, as well as the costs related to prolonged ELR versus ILR assessments balanced with potential reduction in recurrent stroke with early targeted OAC therapy are all important and unanswered questions which this aspect a pivotal trial will address. The pilot phase will assess whether a pivotal trial is warranted and collect important interim data

2.0 STUDY OBJECTIVES

The aim of the pilot is to assess feasibility of a pivotal trial. If successful, we will proceed with a pivotal trial assessing cost-effectiveness. The pilot will assess feasibility in terms of recruitment, data collection, and rates of clinically actionable rhythm detection; that is identification of an atrial arrhythmia that results in initiation of additional anti-platelet or OAC therapy as per usual clinical practice. Unlike prior studies, this trial will include stroke/TIA patients without known AF with both cryptogenic and known stroke mechanisms.

2.1 Hypotheses:

1. Both strategies are feasible and can be implemented in a large geographic region (Alberta).
2. The implantable loop recorder (ILR) plus remote monitoring will diagnose more paroxysmal AF / atrial flutter and provide better assessment of the total burden of

AF resulting in a greater proportion of patients started on an OAC versus the external loop recorder (ELR) strategy.

3.0 METHODS

3.1 Study Design: Randomized, open label trial comparing two different extended ECG monitoring strategies for the detection of paroxysmal AF / atrial flutter after ischemic stroke or transient ischemic attack (TIA).

3.2 Selections of Subjects

Inclusion Criteria:

1. Informed consent from the patient
2. Age \geq 18 years
3. Diagnosis of the index event* made by a stroke specialist of an acute ischemic stroke or TIA occurring within the last 6 months. The event must be either:
 - i) arterial ischemic stroke confirmed by neuroimaging; or ii) transient ischemic attack with DWI positive lesion on MRI
4. The patient is expected to survive at least 6 months
5. At least one 12-lead ECG has already been obtained as part of the routine clinical post-stroke/TIA work-up, and no ECGs have shown any episodes of atrial fibrillation or atrial flutter
6. The patient is being actively investigated for the etiology of the stroke/TIA event and additional cardiac monitoring is desired to screen further for the possibility of occult paroxysmal atrial fibrillation/flutter

Exclusion Criteria:

1. Previously documented atrial fibrillation/flutter.
2. Planned carotid endarterectomy or carotid artery stenting within 90 days.
3. Any condition for which there is already an evidenced-based indication for long term OAC.
4. Pacemaker or ICD device that would allow for detection of AF / atrial flutter.
5. Work-up for stroke that has already included extended (>48 hours) external ECG.
6. Stroke and/or comorbid illness will prevent completion of planned follow-up assessments.

3.3 Study Enrollment Process

The study will be conducted over 24-30 months. A total of 300 patients will be recruited during from inpatient stroke units and stroke prevention clinics at the Foothills Medical Centre, University of Alberta Hospitals, and Grey Nuns Community Hospital using standard of care screening methods. Eligible patients will be randomized in a 1:1 ratio to receive either an ILR coupled with remote monitoring for 12 months versus an ELR for 30 days. A centralized web based randomization process will be used. Patients will be randomized in

small, variable block sizes. Both groups of patients will receive the best standard of care for secondary stroke prevention based on the Canadian best practices guidelines.(12)

Monitoring with ELR for 30 days

The ELR group will be fitted with a battery operated SpiderFlash-t (Sorin Group, USA) auto-triggered ELR and will be provided with a diary to track total hours worn per day and any clinical symptoms.

ILR with remote monitoring for 12 months

The ILR plus remote monitoring group will have a Health Canada approved Medtronic Reveal LINQ device surgically implanted. This is a miniaturized recorder about the size of a clip on a pen (44.8 mm x 7.2 mm x 4.0mm) (Figure 1a). It can be readily inserted in a procedure room with a very low risk of complications. It will be linked to a wireless (cellular) remote monitoring system (MyCareLink) (Figure 1b).

3.4 Study Assessments (see Appendix I)

Baseline Visit (Day 0)

During this visit patients will be assessed for eligibility. Demographic information, medical history, vitals, height, weight, antithrombotic medication, diagnosis of stroke subtype (using the Oxfordshire Classification of Stroke Program; OCSP), etiology (using the Test of Orgaran in Stroke Trial (TOAST) criteria)(13), and a calculation to determine stroke risk related to atrial fibrillation (CHA2Ds2-VASC) will be collected and recorded in a case report form (CRF). Baseline stroke severity (NIHSS), health status (EQ-5D), and global disability (modified Rankin scale using structure interview)(15) will also be completed. The results of etiologic investigations performed prior to enrolment and as part of clinical care including Holter monitor, echocardiography, neuroimaging (CT and/or MRI) and vascular imaging will be collected.

Patients who are randomized to receive 30-day cardiac event monitoring will be asked to complete a patient diary on a daily basis to monitor the daily number of hours the monitor is worn.

Day 30 (± 7 days)

This visit will be used to collect information about etiologic investigations related to the index stroke completed since the baseline visit. The study physician will determine if there has been any new stroke / TIA and cardiac events, new diagnoses of atrial fibrillation, and changes in medications including antithrombotic agents. In patients with the ILR the implantation site will be examined. In addition, patients will have vital signs completed and an ECG.

6 month (± 2 weeks) Follow-Up

This visit may be completed by Telephone call or in clinic. During this visit subject detailed review of medical history. Blood pressure and pulse will be obtained at this visit. EQ-5D and modified Rankin will be repeated. New diagnosis of atrial fibrillation, stroke / TIA,

cardiac events and current antithrombotic medications will be recorded. 12-lead ECG will be obtained.

If the visit is completed via the phone: Blood Pressure and Pulse will be obtained if the subject has a home Blood pressure cuff, otherwise this will not be collected. The EQ-5D will be completed over the phone and the caller will record the subject's response. The subject will be asked to go for an ECG after the call has been completed.

1 and 2 year (\pm 4 weeks) Follow-Up

This visit will be conducted by telephone. Patients will be contacted to collect data about any new diagnosis of atrial fibrillation, stroke / TIA, cardiac events and changes in antithrombotic medications.

4.0 STUDY OUTCOMES

Primary Outcome

The primary outcome will be the rate of detection of an atrial arrhythmia (AF / atrial flutter) that results in initiation of additional anti-platelet or OAC therapy as per usual clinical practice.

Secondary Outcomes:

1. Recruitment rates.
2. Compliance with assigned therapy (accept ILR, conduct at least 80% of ELR assessments)
3. Time to detection of first episode of atrial fibrillation / atrial flutter \geq 30 seconds.
4. Costs for all cardiac and non-cardiac investigations related to etiologic workup of index stroke / TIA.
5. Total duration of any detected atrial fibrillation / atrial flutter.
6. Study related adverse events / serious adverse events.
7. Clinical recurrence of ischemic stroke / TIA, death, hemorrhagic stroke, major adverse bleeding, or death.
8. Association between baseline clinical characteristics (e.g. comorbidities, burden of supraventricular ectopy on Holter, left atrial dimension) and subsequent detection of AF

OUTCOME REPORT

If a subject experience any of the following a outcome report is to be completed following:

- New TIA – complete GUSTO
- New Ischemic Stroke – complete TOAST
- Intracranial Hemorrhage- Complete Intracranial Hemorrhage classification

- Other Bleeding event- complete GUSTO
- Newly Diagnosed Atrial Fibrillation/Atrial Flutter

Assessment of Adverse Events

All serious adverse events (per GCP guidelines) will be reported and described using the MEDRA classification and categorized as related or unrelated to the treatment strategy.

5.0 STATISTICAL METHODS

Sample Size and Power Calculation

A total of 300 patients will be randomized in the pilot phase. This sample size reflects 8% inflation for cross over (2% with either strategy) and loss to follow-up (5% in each group). This sample size provides 85% power to assess a clear difference in rates of atrial arrhythmia (AF / atrial flutter) that results in initiation of additional anti-platelet or OAC therapy between the two strategies (two- sided alpha of 5%). This estimate is based on the following assumptions:

1. Equal allocation (1:1) to ELR for 30 days vs. ILR plus remote monitoring for 12 months.
2. 10% rate of AF / atrial flutter that results in initiation of additional anti-platelet or OAC therapy in the ELR and 20% rate of this endpoint in the ILR plus remote monitoring group.

This estimate was derived using the Two Independent Proportions (Null Case) Power Analysis estimation method (PASS 2012).

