2.0 ANALYSIS POPULATIONS**2.1 Intent-to-Treat Population**

The study will be analysed by intention to treat (intention to monitor, in this case).

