5.0 STATISTICAL METHODS

The software used for all summary statistical analyses will be STATA v16.1.

Percentages will be rounded to one decimal place, except 0% and 100% will be displayed without any decimal places. Minima and maxima will be rounded to the precision of the original value; means and medians will be rounded to one decimal place greater than the precision of the original value; SDs will be rounded to two decimal places greater than the precision of the original value. P-values will be reported to four decimal places (0.xxxx), with values less than 0.0001 presented as <0.0001.

Inferential analyses will generally include statistics such as 2-sided 95% confidence intervals (CI), and p-values. Unless stated otherwise, all statistical tests will be 2-sided Subject Disposition.

The primary outcome (atrial fibrillation) and the first composite secondary outcome (atrial fibrillation or death) will be analysed by intention to treat, using time-to-event analysis. Secondary outcomes will be reported as proportions.

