6.1.3 Primary Efficacy Analysis

Two sample comparison of proportions or patients reaching the primary outcome at one year, unadjusted.

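### The stated 85% power does not follow from the plan's own inputs: 300 patients at 10% versus 20% give about 68%, or about 62–65% after crossover and loss to follow-up

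*Protocol*

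**What the plan says.** Protocol section 5.0 (Sample Size and Power Calculation) plans 300 patients, randomised 1:1. It assumes that 10% of the ELR group and 20% of the ILR group have an atrial arrhythmia that leads to added antithrombotic therapy, and it sets a two-sided alpha of 5%. It then claims: "This sample size provides 85% power to assess a clear difference in rates of atrial arrhythmia (AF / atrial flutter". The 300 is said to contain an allowance already: "This sample size reflects 8% inflation for cross over (2% with either strategy) and loss to follow-up (5% in each group". The method is named: "This estimate was derived using the Two Independent Proportions (Null Case) Power Analysis estimation method (PASS 2012". SAP section 1.4 carries the same inputs and the same 85%.

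The planned analysis is of the same type as the calculation. SAP section 6.1.3 specifies: "Two sample comparison of proportions or patients reaching the primary outcome at one year, unadjusted". SAP section 2.1 sets the population: "The study will be analysed by intention to treat (intention to monitor, in this case". SAP section 5.0 also says that the primary outcome "will be analysed by intention to treat, using time-to-event analysis", and SAP section 6.1.2 frames the hypothesis as a hazard ratio above 2.0.

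**The concern.** For 10% versus 20%, 150 patients per arm is well short of what 85% power normally requires, even before any allowance for attrition. Here the total, the allocation, both rates, the alpha and the type of test are all stated, so the figure can be checked without outside information.

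The power paragraph is the only statistical justification given for 300. If it is wrong, a non-significant result would be read as coming from a trial with a 15% chance of missing a doubling of detection, when that chance is more than twice as large. No passage makes progression to the pivotal trial depend on a significant between-arm test, so the consequence lies in how the result is read and not in that decision.

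**Working it through.** **Inputs** (Protocol 5.0, SAP 1.4): n = 150 per arm; p1 = 0.10 (ELR); p2 = 0.20 (ILR); two-sided alpha 0.05, so z = 1.960; 2% crossover with either strategy; 5% loss in each group; 8% inflation overall.

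**Formula.** Two independent proportions, normal approximation, pooled variance under the null:

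power = Φ[(p2 − p1 − z·s0) / s1], where s0 = √(2·p̄(1 − p̄)/n), s1 = √((p1(1 − p1) + p2(1 − p2))/n) and p̄ = (p1 + p2)/2.

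**Attempt to reproduce 85%, all 300 analysed.**
- p̄ = 0.15; s0 = √(0.255/150) = 0.04123; s1 = √(0.25/150) = 0.04082.
- (0.10 − 1.960 × 0.04123)/0.04082 = (0.10 − 0.08081)/0.04082 = 0.470.
- Φ(0.470) = **68.1%**.

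**Other versions of the calculation, 150 per arm**

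| Version | Power |
|---|---|
| Unpooled variance | 68.8% |
| Arcsine | 69.1% |
| Exact enumeration of the pooled z test | 68.6% |
| Continuity-corrected | 62.0% |
| Fisher exact | 62.9% |
| One-sided 5% (text says two-sided) | 78.5% |
| 300 read as per arm (text says total) | 93.1% |

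None gives 85%.

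**After the plan's allowance.** The documents do not say how the 8% combines loss and crossover, so two readings are shown.

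1. *The full 8% is removed.* 300 × 0.92 = 276 (138 per arm) gives 64.4%; 300/1.08 ≈ 278 (139 per arm) gives 64.7%.
2. *Loss is removed and crossovers stay in, as under intention to treat.* 150 × 0.95 = 142.5 per arm. The rates become 0.98 × 0.10 + 0.02 × 0.20 = 0.102 and 0.98 × 0.20 + 0.02 × 0.10 = 0.198. Then (0.096 − 0.08291)/0.04192 = 0.312, and Φ(0.312) = 62.3%.

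**Sample size for 85%** (z for power = 1.036):

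n = (1.960·√0.255 + 1.036·√0.25)² / 0.10² = (0.9897 + 0.5182)² / 0.01 = 227.4, so 228 per arm, or 456 evaluable. With the diluted rates (10.2% versus 19.8%) it is 246.9, so 247 per arm, or 494.

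**Difference that 300 can detect with 85% power.** With the ELR rate held at 10% and the same formula solved for p2, the ILR rate must be 22.7% (all 300 analysed), 23.3% (139 per arm) or 23.8% (5% loss plus 2% crossover dilution).

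**Time-to-event reading.** Expected events are 150 × 0.10 + 150 × 0.20 = 45. The Schoenfeld approximation, power = Φ[√(45/4)·ln(HR) − 1.960], gives 64% at HR 2.0. At the hazard ratio implied by the two rates, ln(0.8)/ln(0.9) = 2.12, it gives 71%. Both assume proportional hazards. That is implausible when patients "receive either an ILR coupled with remote monitoring for 12 months versus an ELR for 30 days".

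**The case against.** Four arguments can be made for leaving the text alone.

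- *This is a pilot feasibility study.* A pilot may have low power for a between-arm test, and nothing here asks for more patients. But the plan makes an explicit 85% claim for its primary outcome, and the SAP labels that comparison the primary efficacy analysis. The pilot label does not make the figure correct.
- *One input may simply be a typing error.* This is possible and cannot be excluded without the software output. An ELR rate of 8%, for example, would give 85.3% at 150 per arm, but only about 80–83% after the allowance that the 300 is said to include. Nothing in the documents points to 8%. In either case the printed inputs and the printed power do not fit together.
- *The post-allowance figure is uncertain.* This stands in part. Ignoring crossover and removing only the 5% loss gives 65.8%. Removing 8% and also diluting the rates gives 60.9%, which counts crossover twice. SAP 6.1.3 does not name the test, and a continuity-corrected or Fisher test would give about 58–59% at 138 per arm. All of these are far below 85%.
- *Correcting the figure changes nothing that is done.* True for enrolment, conduct and analysis. It does change how a null result should be read.

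**Conclusion.** The concern holds and the statement must be corrected. On the plan's own inputs, power is 68%, which is 17 percentage points below the stated 85%. After the allowance it is about 62–65%, a gap of 20 to 23 points. The type II error is about 32% (35–38% after the allowance), against the 15% implied. The 68% rests only on figures printed in both documents and on the unadjusted comparison of proportions that the SAP plans. The 62–65% also depends on how the 8% is read. Which printed entry is wrong cannot be settled from the documents.

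**What to change.** Keep 300 and check the original PASS 2012 inputs.

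Unless an input was mis-transcribed, replace the power statement in Protocol 5.0 and SAP 1.4 with wording such as:

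> For the unadjusted two-sample comparison of proportions at one year, 300 patients give about 68% power (about 62–65% after crossover and loss to follow-up) to detect 10% versus 20% at a two-sided alpha of 5%. Power of 85% is reached only for a larger difference, such as 10% versus about 23% (23–24% after crossover and loss).

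If an input was mis-transcribed, correct it in both documents and recompute the power from it, including the allowance.

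Add one sentence on what the rates refer to. The 10% and 20% were set for arrhythmia that leads to a change of therapy. The Protocol's change summary records for 4.0r that "the primary outcome was defined as definite atrial fibrillation lasting 2 minutes or more, including atrial flutter", and no separate rates are stated for that endpoint. The arithmetic above does not depend on this.

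The cost is a check of one file and one paragraph in each document. The only drawback is a less favourable stated power.
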